Surgical service lines will include orthopedic total joint, orthopedic spine, gynecology/oncology, thoracic, general, hernia, colorectal, open vascular, plastic, and open urological procedures. These lines will be randomized 1:1 to either the bundle of activities or usual care. The unit of randomization is the service line. The perioperative environment (the patient, the patient to follow, and all providers caring for the patient and the patient to follow) for the randomized service line (treatment or usual care) will be involved in surveillance. This means that all patients, all providers caring for those patients (changes day by day), and care environments (equipment and stopcock sets) will be involved in surveillance. Surveillance from treatment and control groups will yield *S. aureus* transmission events that will be processed to guide proactive improvements in the treatment bundle.

Treatment group (bundle) inclusion/exclusion criteria:

Inclusion criteria: Patients seen at UIHC who are scheduled to undergo surgery from providers in one of the service lines above, documentation of informed, written consent, >18 years of age, procedure requiring general/regional anesthesia.

Exclusion criteria: Lack of documented informed, written consent, patients <18 years of age, procedures outside of the surgical service lines listed above, not requiring general/regional anesthesia, patients not seen in the UIHC clinics, and an allergy to iodine/shellfish or chlorhexidine.

Usual care group (existing practice at UIHC) inclusion/exclusion criteria:

Inclusion criteria: Patients seen at UIHC who are scheduled to undergo surgery from providers in one of the service lines above, documentation of informed, written consent, >18 years of age, procedure requiring general/regional anesthesia.

Exclusion criteria: Lack of documented informed, written consent, patients <18 years of age, procedures outside of the surgical service lines listed above, not requiring general/regional anesthesia, patients not seen at UIHC, and an allergy to iodine/shellfish or chlorhexidine.

VI.14

Provide an estimate of the total number of subjects that would be eligible for inclusion in each of your study populations (include your control population if applicable)

We anticipate that >80% of all patients undergoing surgery in the surgical service lines above will be eligible for the study.

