We do not know what the service line will be for the treatment and control until we randomize. We do not know exactly how many patients each line will see over the next 2 years. There are 24,000 patients that undergo adult surgery at UIHC each year. Over two years, that is 48,000 patients. The lines selected in total represent >80%, at least 38,400. That is 3840 per line, or roughly 1500 patients each year per line. Thus, we expect that 80%, or roughly 1200 patients, will be eligible for the study for each line over the 2 year period. In terms of providers, approximately 10 providers will be involved in the care of each patient in the OR and discharge area combined. Thus, over two years, there will be 12,000 providers (not exclusive; as providers may be repeatedly sampled over the two year period).

Treatment group (bundle): 80% of all patients in the randomized service lines are expected to be eligible, N=1200 for each service line. We expect participation from the majority (>80%) of providers in the OR and in the discharge area, N=12,000 providers for each line.

Usual care group: 80% of all patients in the randomized service lines are expected to be eligible, N=1200 for each service line. We expect participation from the majority (>80%) of providers in the OR and in the discharge area, N=12,000 providers for each line.

VI.15

Describe how you will have access to each of your study populations in sufficient number to meet your recruitment goals.

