 - Improved environmental cleaning: Environments (OR and ward) affected by high-risk S. aureus transmission events will be mapped by surveillance and addressed by automated reporting to the anesthesia workroom supervisor. This will trigger improvements in routine (standard cleaning using quaternary ammonium compound and micro cloth followed by a surface disinfection wipe) and terminal [improved routine technique followed by employment of robotic cleaning (Ultraviolet light)] cleaning.
- Fatigue mitigation: The team will use surveillance to continually monitor the impact and fatigue of the proposed interventions as conveyed by failure mode analysis of transmission dynamics involved clonal S. aureus transmission.

XI.2

Provide the rationale or power analysis to support the number of subjects proposed to complete this study.

Statistical Analysis: The unadjusted primary intention to treat analysis will compare the proportion of clonally-related S. aureus transmission events occurring in treatment vs. control perioperative (preoperative, intraoperative case pair, and postoperative) observational units across the 6 randomized service lines using the Chi squared test. We will assess for balance for variables known to be associated with intraoperative

transmission (case, duration > 2 hours, and discharge location). In the case of imbalance, we will use multivariate techniques to further explore the treatment effect using a generalized linear models approach.

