Initial Power Analysis (see amendment below based on reviewer concerns): We intend to screen a total of 1000 patients for up to 10 surgical service lines. Service lines will be randomized 1:1, yielding 500 patients in each treatment arm. Each patient will provide 4 observational units that include preoperative to intraoperative, intraoperative case 1 to intraoperative case 2, intraoperative case 1 to postoperative, and preoperative to postoperative opportunities for detection of *S. aureus* transmission. Thus, 500 patients in each arm will provide 2,000 observational units for a total of 4,000 observational units during the two-year study period. We originally calculated that this provided 90% power to detect a 30% relative reduction in the primary outcome (10.58% down to 7.41%). The estimated clonally related *S. aureus* transmission rate was based on a previously reported detection rate of 58 events in 548 observational units for all-comers to the operating room at 3 major academic medical centers in the United States. To address service line variation, we supposed that the logit-frequencies of the primary outcome for each service line were distributed as a normal distribution with a mean of -0.41 and standard deviation of 0.20. This amount of between-line variation corresponds to an intra-cluster correlation (ICC) of approximately 1%. It can also be interpreted as the amount of variation in which service lines in the top quartile of rates would have an average frequency (after removing within subsection binomial variation) of 46% while service lines in the lowest quartile have an average frequency of 33%. These calculations were accomplished using Monte Carlo simulations written in R 3.3, and using in part the following approximation for the ICC when rates are logit-normal, $1/(1+1/\sigma^2 \cdot \pi^2 \cdot \text{pa}(1-\text{pa}))$ (which can be readily derived using the delta theorem) where pa is the average frequency across centers and σ^2 is the standard deviation on the logit scale. We calculated that this provides 85% power to detect a 30% relative reduction in the primary outcome (40% down to 28%) if there is significant variation between service lines. If indeed there is no variation between service lines, the power is 98%.

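### The primary analysis names six randomised service lines where the rest of the protocol points to ten; the 85% power best fits ten, is not delivered at six by any test tried that holds 5%, and is not secured by the pilot

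*Protocol*

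**What the plan says.** **Number of randomised units.** Protocol VI.13 makes the service line the unit of randomisation, names ten lines and says "These lines will be randomized 1:1 to either the bundle of activities or usual care". VI.14 takes at least 38,400 patients over two years and continues "That is 3840 per line, or roughly 1500 patients each year per line"; 38,400 / 3840 = 10. The Initial Power Analysis in XI.2 says "We intend to screen a total of 1000 patients for up to 10 surgical service lines". The Statistical Analysis paragraph of XI.2, which defines the primary comparison, runs it "across the 6 randomized service lines using the Chi squared test", unadjusted.

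**Power.** XI.2 assumes line logits that are normal with "mean of -0.41 and standard deviation of 0.20", an ICC of about 1%, and 500 patients per arm. It reports: "We calculated that this provides 85% power to detect a 30% relative reduction in the primary outcome (40% down to 28"%). It adds: "If indeed there is no variation between service lines, the power is 98"%. The same paragraph also says that "500 patients in each arm will provide 2,000 observational units", so the unit behind 85% is not explicit. No line count, test or alpha is attached to the 85%.

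**Pilot.** XI.2 reports transmission in 28% of orthopedic and 58% of gyn/onc cases, using possible intraoperative events not yet shown to be clonal. It takes this as support for the assumed variation and the power, and expects less variation after genomic analysis.

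**SAP.** It uses two-sided P < .05 and repeats a Poisson model with clustering by surgeon or specialty. It gives no line count and no power.

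**The concern.** When whole service lines are randomised, the number of lines largely drives power. The paragraph that defines the primary analysis and the sections that describe the design disagree on that number, and nothing in the SAP settles it. The 85% and the pilot are also the protocol's answer to reviewers who questioned service-line variation. If that answer rests on ten lines and only six are randomised, the trial is weaker than stated and a null result could be misread as no effect. Separately, the test named as primary ignores the lines, so under either count it would reject a true null far more often than 5%.

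**Working it through.** **Inputs.** From XI.2: 40% vs 28%, 500 per arm, logit mean -0.41, SD 0.20. From the SAP: two-sided 0.05. Assumed: patients split evenly over lines.

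**1. The no-variation figure.**
- Pooled rate 0.34. SE under the null = sqrt(2 × 0.34 × 0.66 / 500) = 0.02996. SE under the alternative = sqrt((0.24 + 0.2016) / 500) = 0.02972.
- Power = Φ((0.12 − 1.96 × 0.02996) / 0.02972) = Φ(2.06) = 0.980, as stated.
- With 2,000 independent units per arm the same formula gives 1.00. The 98% therefore rests on 500 per arm.

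**2. The ICC.** With σ² = 0.04 and pa(1 − pa) = 0.24, ICC = 1 / (1 + 1/(0.04 × 0.24)) = 0.0095, as stated (about 1%).

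**3. Design effect, ICC treated as known.** DE = 1 + (m − 1) × ICC.
- Ten lines: m = 100, DE = 1.94. Six lines: m = 500/3, DE = 2.57.
- Multiplying both variances in step 1 by DE gives power 0.82 at ten lines and 0.71 at six.

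**4. Simulation.** Line logits were drawn from N(-0.41, 0.20). Each range runs from a constant odds ratio to a treated rate of 0.7 × the line rate. Main cells used at least 60,000 runs. The random-intercept logistic model used 3,000 (2,000 under the null), and multilevel Poisson used 5,000 (7,000 under the null).

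| Test | Power, ten lines | Power, six lines | Loss (points) | Type I error, ten / six |
|---|---|---|---|---|
| Unadjusted chi-squared (protocol primary) | 0.93–0.94 | 0.90–0.92 | about 3 | 0.16 / 0.22 |
| Uncorrected sandwich z | 0.87–0.89 | 0.82–0.85 | 4–5 | 0.13 / 0.19 |
| Random-intercept logistic, Wald z | 0.86–0.88 | 0.81–0.83 | 4–5 | 0.10 / 0.14 |
| Multilevel Poisson by line, Wald z | 0.83–0.86 | 0.78–0.80 | 5–6 | 0.056 / 0.088 |
| Random-intercept logistic, likelihood ratio | 0.82–0.85 | 0.72–0.76 | 9–10 | 0.076 / 0.107 |
| Line rates, 1.96 cutoff | 0.82–0.85 | 0.72–0.76 | 9–10 | 0.086 / 0.122 |
| Design-effect chi-squared, ICC known | 0.82–0.84 | 0.70–0.72 | 12 | 0.050 / 0.050 |
| Random-intercept logistic, t reference | 0.78–0.81 | 0.60–0.63 | 18 | 0.050 / 0.050 |
| Line-level t-test | 0.73–0.76 | 0.49–0.53 | 23–24 | 0.049 / 0.051 |

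At ten lines several cluster-adjusted tests land on or near 85%. At six lines only the sandwich z and the Wald z come close (0.85 and 0.83, both under the 0.7 × rate definition), with type I error of 0.19 and 0.14.

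**5. Sensitivity to SD.** At SD 0.40 the line-level t-test has power 0.38–0.44 at ten lines and 0.22–0.25 at six.

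**6. The pilot.**
- Gap = logit(0.58) − logit(0.28) = 0.323 + 0.944 = 1.267.
- SE = 0.533 if 44 and 24 cases are independent, or 0.753 for 22 and 12 pairs (denominators assumed).
- SD estimate = sqrt((1.267² − SE²)/2) = 0.81 or 0.72. With whole event counts inferred from the percentages it is 0.76–0.85.
- 95% limits come from gap² / (2·SD² + SE²) as chi-squared with 1 df. The lower limit is 0.13 by case and 0 by pair (0 to 0.17 with inferred counts). The upper limit is above 28.
- If SD is 0.20, the P value for a gap this large is 0.036 by case or 0.115 by pair.

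**The case against.** **The six may be a leftover.** Two sections give ten and the power paragraph allows ten, and every six-line loss depends on that one figure being right. This stands, so those losses are conditional. It does not remove the need to settle the count, because the figure sits in the definition of the primary analysis.

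**No arithmetic error is shown.** The 98%, the ICC and, at ten lines, the 85% all reproduce. A reader might infer that 85% is miscalculated, or that it can only have come from ten lines. The documents support neither: they name no test or line count, and two anti-conservative tests reach 83–85% at six.

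**The protocol's own test barely changes.** The chi-squared test loses only about 3 points. That is true, but a test that rejects a true null 16–22% of the time does not deliver power at 5%. The same standard applies to the 1.96 cutoff behind the best match to 85% (type I error 0.086 at ten lines).

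**The SAP's multilevel Poisson might rescue the figure.** If specialty means line and the outcome is yes/no per pair, it gives 0.83–0.86 at ten lines with type I error 0.056. That near-5% level reflects offsetting errors. Poisson standard errors are too wide for a binary outcome: at a 40% rate without clustering, the effective cutoff is 1.96/sqrt(0.6) = 2.53, a type I error of about 0.011. At six lines the error is 0.088, so it offers no valid rescue there.

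**Equal line sizes are an assumption.** This stands. With an illustrative split of 270/120/60/30/20 per arm (my assumption), ten lines give about 0.65 with the 1.96 cutoff and 0.53–0.55 with the t-test. The ten-line figures are themselves conditional.

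**The pilot comes with a caveat.** The authors expect less variation once clonality is tested, and the orthopedic group pools two of the listed lines. Both points stand. A reader might infer that the pilot refutes SD 0.20, but its interval is too wide for that, and treating paired cases as independent overstates the evidence.

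**Conclusion.** The point holds as an unresolved conflict in the number of randomised units, together with a power figure that the named primary test does not deliver at a true 5% level. The 85% is best matched by ten lines with a normal-reference test, without being unique to that setting.

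If six lines are randomised, no test tried that holds 5% exceeds about 0.72, against 0.82–0.84 (design effect, ICC known) and 0.73–0.76 (line-level t) at ten. The loss across cluster-adjusted tests is about 4–24 points. If ten is right, the main repairs are one number, a label on the 85%, and the choice of primary test.

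The excess type I error of the unadjusted chi-squared test applies under both counts. The pilot leaves SD 0.20 neither confirmed nor clearly excluded. These sizes assume equal line sizes, SD 0.20, 500 pairs per arm and the SAP's two-sided 0.05. This should be fixed; it does not show that the trial has six lines or that its power is about 50%.

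**What to change.** - State one number of randomised lines, and make VI.13, VI.14 and both parts of XI.2 agree with it.
- Say that 85% and 98% use 500 pairs per arm. Name the line count, the test and the effect definition (constant relative reduction or constant odds ratio) behind 85%.
- Replace the unadjusted chi-squared test as primary with a line-aware analysis that has a small-cluster reference, and name the same analysis in the SAP.
- Restate power for that analysis at the confirmed line count, over a range of SDs and with the line-size assumption stated. For a line-level t-test at SD 0.20 with equal sizes, this is about 0.73–0.76 at ten lines or 0.49–0.53 at six.
- Keep 85% only if ten lines is confirmed, labelled as a normal-reference figure with type I error above 5%.
- In the pilot paragraph, replace the claim of support with: The pilot had two main lines and a non-clonal intraoperative outcome, and is too small and too different in outcome to confirm the assumed between-line variation; clonal variation may be smaller.

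The cost is a lower stated power, a changed primary test and a re-run of the existing simulation. No patients are added.

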Reducing Perioperative S. aureus Transmission via use of an Evidence-Based, Multimodal Program Driven by an Innovative Software Platform (OR PathTrac)

9/20/2018

Statistical Analysis

Multiple statistical methods were used. For simplification, we list the statistical methods in the precise sequence they are reported in the results.

The Fisher exact test was used to compare patient and procedural demographic information for treatment vs control groups and for cases involving *S* aureus transmission. Similarly, the distribution of patients by ASA scores greater than 2 and by sex for enrolled vs eligible patients were compared by surgeon using the Mantel-Haenszel test.

The Fisher exact test was also used to examine the potential association of each of the covariates mentioned earlier with *S aureus* transmission. None were associated.

A 2-sided Wilcoxon-Mann-Whitney test was used to examine the association of treatment assignment with the number of transmitted *S aureus* isolates. Poisson regression was used to estimate the incidence risk ratio (IRR) of *S aureus* transmission for the independent variable of treatment. Poisson regression was used to estimate the IRR because the incidence of transmission was so large (ie, much greater than 10%) that the odds ratio estimated using logistic regression would be a biased estimator of the relative risk.²⁴ We repeated the analysis using multilevel Poisson regression clustering by surgeon or specialty.

The Fisher exact test was used to compare the proportion of patients in the treatment group with transmission events before vs after surveillance feedback and the proportion of patients with SSI with and without documented *S aureus* transmission. Poisson regression was used to compare the proportion of patients with SSI with and without documented *S aureus* transmission, clustered by surgeon.

The proportion of patients with SSIs was compared with the Fisher exact test. Time to infection was evaluated by Cox proportional hazard modeling. We repeated the analysis using multilevel Poisson regression clustering by surgeon and specialty.

There were no missing data for the primary and secondary outcomes. Calculations were performed using Stata version 16.1 (StataCorp). All P values were 2-sided, and P < .05 was taken to indicate statistical significance.

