Vascular care: Each patient in the treatment group will receive the Ultrapore zero (BBraun Medical) closed, disinfectable stopcock set and the DOCit and HubScrub disinfection system (Saxa Medical). The DOCit is a cap that providers in the OR will insert syringes into to keep them free of environmental contamination, organized, and sterile given the 62% isopropyl alcohol in each cap. This is a FDA approved device that is on the market. It has been shown to reduce infections with a number needed to treat of 16. The HubScrub is a cap with the same disinfectant that providers will use to scrub the injection ports, or stopcock sets. This cap contains 62% alcohol and brushes for mechanical disruption of biofilms. The cap disinfects the port in 10 seconds, maintains disinfection for >72 hours when covered, and only needs to be turned 2 times to disrupt any biofilm. It is also evidence based and proven to reduce infections. It is also FDA approved and on the market. The DOCit and HubScrub systems will be provided in the preoperative area, affixed to the IV pole for easy access by the anesthesia provider in the OR, and transported with the patient to the recovery unit.

Hand Hygiene: The Saxa system also contains a single-handed hand hygiene device that allows the provider to disinfect their hands at every opportunity. It is affixed to the IV pole and will be used preoperatively, intraoperatively, and postoperatively.

Environmental cleaning: Surveillance will map ORs affected by residual contamination with hyper transmissible, resistant, and virulent organisms. This information will be communicated to the environmental cleaning service in the OR electronically, automatically updated each day, in order to guide improved routine and terminal cleaning for affected ORs. Improved routine cleaning will involve use of the conventional quaternary ammonium compound with a microfiber cloth followed by a surface disinfection wipe. Improved terminal cleaning will involve robotic cleaning using UV robots (using UV light in the OR for under an hour) at night/morning if not being used, or will involve increased duration of application of the previously described cleaning procedure.

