Kits will be transported to RDB Bioinformatics laboratory for processing following sample acquisition. The dynamic surveillance software platform will guide proven, systematic phenotypic and genomic processing of collected samples in order to identify clonal transmission events occurring within and between operating room reservoirs in the observational unit (case pair). Guidance will be based on the strength of epidemiological-relatedness as follows: A transmission event will be defined as the presence of one or more isolates in a measured reservoir that was not present at case start. Transmission events within an observational unit will be further analyzed as directed by the RDB platform to identify clonally-related *S. aureus* transmission events.

The RDB Bioinformatics software platform will process transmission dynamics in order to continually summarize the epidemiology of *S. aureus* transmission. This information will be continually displayed in order to identify the most common reservoir of origin, the most common transmission locations (vectors), the most common mode of transmission (vertical or horizontal), and involvement of key portals of entry (stopcocks). To address strain characteristics, reports will focus on more pathogenic strains defined by the top 5 most transmissible, resistant, and virulent strain characteristics.

Automated analysis reports for overall transmission and for transmission of more pathogenic strains will be used by the infection control perioperative team to continually optimize the interventions affecting all patients in the treatment clusters as described further below. The platform will automatically quantify transmission events occurring in

treatment and control clusters such that involved in data collection and data entry will be blinded to the primary outcome.

All data will be analyzed by the statistician ([name]) at Dartmouth Hitchcock Medical Center who will not be involved in data collection.

Work flow: Monday-Friday only. Limited to patients that are seen in UIHC clinics. 1,000 case pairs: (500 treatment and 500 usual care) will be studied during the 2-year study period. This corresponds to one case pair in the “bundle” group and one case pair in the usual care group each day (5 days a week for 50 weeks each year). All patients will be followed for 90 days for infection development.

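### The SAP carries the protocol's date but was written with outcome data known; it omits the planned primary test and applies P < .05 to analyses not documented as prespecified

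*SAP*

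**What the plan says.** **SAP.** The header date is 9/20/2018, the same as on the protocol's first page. The text is in the past tense and explains its order: "we list the statistical methods in the precise sequence they are reported in the results". It reports three things about the outcomes:
- On covariates and transmission: "None were associated".
- On the choice of model: "Poisson regression was used to estimate the IRR because the incidence of transmission was so large (ie, much greater than 10" per cent).
- On completeness: "There were no missing data for the primary and secondary outcomes".

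It closes with one threshold for everything: "All P values were 2-sided, and P < .05 was taken to indicate statistical significance".

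**Protocol.** XI.1 (Work flow) states that "1,000 case pairs: (500 treatment and 500 usual care) will be studied during the 2-year study period". VII.E.6 adds 90 days of follow-up for infection. XI.2 opens its analysis paragraph with "The unadjusted primary intention to treat analysis will compare the proportion of clonally-related" transmission events by the chi-squared test. It allows a generalized linear model if listed covariates are imbalanced. Section I.5 names superficial and deep SSI as a secondary objective, without a test. The protocol states no alpha.

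On feedback, VII.E.6 describes OR contamination maps as "automatically updated each day", and XI.1 describes monthly stopcock reports and continual improvement cycles. Neither document dates the start of feedback.

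**The concern.** A reader who sees a SAP dated before the data will take its tests, model family, clustering level and before/after split as fixed in advance, and will read each P value below .05 on that footing. If the document was in fact written from the results, the date gives no such assurance.

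Two things are then at stake. The first is whether secondary and within-arm results may be called significant or only described. The second is whether the one comparison that the protocol did commit to can be found at all, since the SAP leaves it out.

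**Working it through.** **1. Could the SAP's facts exist on its date?** The earliest start the documents allow is the ready date in IV.2, 4/01/18. Two years from there is 4/01/2020, and 90 more days gives 6/30/2020, about 21 months after 9/20/2018. Counting from 9/20/2018 itself, the end is 12/19/2020. The protocol of the same date (VI.14) still treats the randomization of lines as to come. A statement that no primary or secondary outcome was missing needs completed follow-up, and a statement that no covariate was associated needs analyzed outcomes. Both must postdate the header.

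The remark on high incidence is weaker evidence. The protocol already expected it: 39% in I.5 and I.6, 40% in the power analysis, and 28% to 58% in the pilot.

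**2. SAP against protocol.**

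| Analysis | Protocol | SAP |
|---|---|---|
| Chi-squared, proportion of clonally related events | Primary (XI.2) | Absent |
| Generalized linear model for treatment effect | Only on imbalance; no family or link | Poisson IRR, unconditional |
| Clustering by specialty | No such model; service line is the randomized unit (VI.13) | Multilevel Poisson |
| Clustering by surgeon | Absent | Multilevel Poisson |
| Wilcoxon on number of isolates | Absent | Present |
| Before/after feedback, treatment arm | Absent | Fisher |
| SSI by transmission status | Absent | Fisher, and Poisson clustered by surgeon |
| SSI by treatment | Objective only (I.5) | Fisher, Cox, multilevel Poisson |
| Threshold .05, two-sided | Absent | All P values |

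**3. Why the chi-squared test should not stand alone.** Service lines are randomized, and the planned test ignores that. First, the protocol's own variance figure. The mean logit of -0.41 gives pa = 1/(1 + e^0.41) = 0.399. With SD 0.20, ICC = 1/(1 + 1/(0.20² × 0.399 × 0.601)) = 0.0095, which reproduces the stated value of about 1%.

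For m pairs per line, design effect = 1 + (m − 1) × ICC, and the false-positive rate of the unadjusted test is about 2 × [1 − Φ(1.96/√DE)].
- 10 lines, m = 100: DE = 1.94, 1.96/1.393 = 1.407, rate 15.9%.
- 6 lines, m = 166.7: DE = 2.57, 1.96/1.604 = 1.222, rate 22.2%.

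Simulation with logit-normal line rates (20,000 trials, 40% in both arms, equal line sizes) gives 15.7% and 22.0%. A t-test on line proportions gives 4.9% in both cases. Both 10 and 6 are used because VI.13 lists ten lines and XI.2 says six.

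**4. The before/after cut.** I simulated 3,000 null series of 500 treatment pairs spread evenly over 24 months, with Fisher's test at .05 and transmission rates of 28% and 40%. One cut fixed in advance, at any month from 3 to 21, gives about 4% to 5%. The better of two cuts (months 3 and 6) gives about 7%, and the best of three (3, 6, 12) about 10%. The best of all 19 monthly cuts gives about 25%; other runs of that case gave 26% to 28%. The last figure is the upper end of this illustration and does not describe what was done.

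**The case against.** The strongest reply is that the SAP is simply the methods text of a finished report under a copied header, that it never calls its analyses planned, and that some of them follow from the protocol. Much of this stands. Poisson regression is a generalized linear model, and a 40% planning rate would have justified avoiding odds ratios before enrolment. Specialty plausibly means service line, so that clustering follows from the design. SSI was a named objective.

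What does not stand is that this makes the date harmless. XI.2 reserves the model for imbalance and names no family or link, and nothing in the protocol covers the remaining additions. A copied header is also best cured by the true date.

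A reader might go further and infer three things that the documents do not support:
- **That the methods were chosen after the data were seen.** The text's date of writing is shown; the date of each choice is not. An earlier version may exist.
- **That the before/after test has a false-positive rate above 25%.** That needs a search over 19 cut dates, and nothing suggests one. The wording names an event, the start of feedback, and a single cut tied to it holds its level.
- **That only the unadjusted chi-squared result may be called significant.** That would favor a test that ignores the randomized unit and demote the SAP model closest to it.

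**Conclusion.** The point holds as one of documentation and labelling. The SAP's text postdates the outcome data, its date says otherwise, the planned primary test is missing from it, and a .05 threshold is spread over analyses that no dated document fixes in advance. The supportable description of those analyses is not documented as prespecified.

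No overall error rate can be given, because the documents do not show how any choice was made. The firm figure is a side condition on the remedy: 16% (10 lines) to 22% (6 lines) for the unadjusted test, assuming the protocol's SD of 0.20 and equal line sizes. The treatment comparison on transmission was planned in substance, and this point does not undermine it. The changes fall mainly on the secondary and within-arm results. Reading specialty as service line is an assumption that the authors should confirm.

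**What to change.** 1. Give the SAP its true date and a version number. If an earlier dated version exists, supply it and mark what it fixed.
2. Report the XI.2 chi-squared comparison of clonally related events and, beside it, a version that accounts for the randomized service lines (the specialty-clustered model). Present the two together as the planned treatment comparison. With so few lines, a line-level t-test is a useful check on the model.
3. Label every other analysis as not documented as prespecified and exploratory, and give estimates with confidence intervals, unless step 1 shows otherwise.
4. Define the before/after cut as the date of the first feedback report logged by the platform, and state that date.

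The cost is wording plus one or two reruns on existing data. The downside is that some secondary results are reported as exploratory.
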